Patient population	
 • Rising PSA after definitive therapy with prostatectomy or radiation therapy (external beam or brachytherapy): 
 ○ Post radical prostatectomy (RP) – AUA recommendation 
 ▪ PSA greater than 0.2 ng/mL measured more than 6 weeks after RP and, ▪ Confirmatory persistent PSA greater than 0.2 ng/mL ○ Post-radiation therapy – ASTRO-Phoenix consensus definition 
 ▪ Nadir + greater than or equal to 2 ng/mL rise in PSA
Rationale for Study	Gallium-68 HBED-CC PSMA has been shown to have a higher sensitivity for the detection of metastatic prostate cancer compared to choline based imaging.
Primary Objective	
 • Sensitivity and positive predictive value (PPV) on a per-patient and per-region-basis of ⁶⁸Ga-PSMA-11 PET for detection of tumor location confirmed by histopathology/biopsy.
Secondary Objectives	
 • Sensitivity and PPV on a per-patient and per-region-basis of ⁶⁸Ga-PSMA-11 PET for detection of tumor location confirmed by histopathology/biopsy and conventional imaging follow-up. • Sensitivity, specificity, and negative predictive value (NPV) on a per-patient basis of ⁶⁸Ga-PSMA-11 PET for detection of tumor location confirmed by histopathology/biopsy and conventional imaging follow-up. • Detection rates on a per-patient basis of ⁶⁸Ga-PSMA-11 PET stratified by PSA value (0.2 - <0.5, 0.5 - <1.0, 1.0 - <2.0, 2.0 - <5.0, 5.0). • Impact of ⁶⁸Ga-PSMA-11 PET on clinical management in BCR patients. • Inter-reader reproducibility. • Safety.
Study Design	This is a phase 1/2 multi-center open label study.
Number of patients	125 patients per year, for three years, giving a total of 375 patients at UCSF. Total population of patients will be 1,500 patients across all institutions.
Duration of Therapy	The study will involve a single imaging study.

Duration of Follow up	The patients will be followed-up by phone one day after the study completion.
Duration of study	The study will reach completion three years from the time the study opens to accrual.
Study Drugs	Gallium-68 labeled PSMA-11 (PSMA-HBED-CC)
Safety Assessments	Patient vital signs will be taken immediately before and after the administration of the radiopharmaceutical. The patients will also be asked to report adverse events.

List of Abbreviations

AE	adverse event

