3.2 Number of Subjects

It is anticipated that 125 patients per year over three years will be enrolled in this study, for a total of 375 at UCSF. In total we aim to enroll 1,500 patients across all sites.

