3.4 Duration of Follow Up

Patients will be followed for one day after the administration of the radiopharmaceutical.

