3.5 Study Timeline

3.5.1 Primary Completion

The study will reach primary completion 36 months from the time the study opens to accrual.

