3.5.2 Study Completion

The study will reach study completion 48 months from the time the study opens to accrual.

4 Study Drugs

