8.2.2 Accrual estimates

We estimate that roughly 125 patients with prostate cancer will be enrolled in this trial per year. Over a four-year period this will result in up to 375 patients being enrolled in the study.

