8.3.2 Analysis of Primary Endpoints

PPVs on a per-patient and per-region-basis of ⁶⁸Ga-PSMA-11 PET for detection of tumor location confirmed by histopathology/biopsy will be calculated and reported along with the corresponding two-sided 95% confidence intervals. The confidence intervals will be constructed using the Wilson score method.

a) Imaging interpretation ⁶⁸Ga-PSMA-11 PET:

PET images will initially be interpreted by a board certified nuclear medicine physician or a board certified radiologist experienced in reading PET at the time of the imaging study at the institution that the study is being performed. These interpretations will not be used for final evaluation. For the data sets included in the analysis for the Primary Endpoint, imaging data will be anonymized and collected at a central site. PET data will be interpreted by three different readers in a random order at separate reading sessions. ⁶⁸Ga-PSMA PET/CT reading training set and guides will be provided and completion of this training will be required for all central review readers.

Visual interpretation:

Regions of suspected disease will be graded on a two-point scale by each reader (0=Negative or 1= Positive). A region will be judged as positive if at least one lesion in this region is visually positive.

- i) Lymph nodes will be considered positive if the ^{68}Ga -PSMA-11 uptake is focal and greater than blood pool (adjacent or mediastinal blood pool). Pelvic lymph nodes will be subclassified according to their localization as follows: R/L obturator, R/L external iliac, R/L internal iliac and other (total of 7 subgroups).
 - ii) Visceral lesions will be considered positive if the ^{68}Ga -PSMA-11 uptake is focal and greater than physiologic background activity of the involvement organ or anatomic site.
 - iii) Bone lesions will be considered positive if the ^{68}Ga -PSMA-11 uptake is focal and greater than physiologic bone marrow.
 - iv) Prostate bed and prostate lesions will be considered positive if the ^{68}Ga -PSMA-11 uptake is focal and greater than physiologic background activity of the involvement organ or anatomic site.
- b) Follow-up Imaging:

All patients will be followed up 3-12 months with conventional imaging (dedicated CT, MRI and/or bone scan). Interpretation of follow-up imaging will be performed by local read. The follow-up conventional imaging should be the same modality/modalities as the initial staging work-up to allow for reproducible and accurate comparisons.

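### The documents give conflicting dates for accrual, completion and follow-up, and only one combination of them leaves room for the 12-month imaging window

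*Combined protocol and SAP*

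**What the plan says.** **Completion.** The abstract (Duration of study) says "The study will reach completion three years from the time the study opens to accrual". Section 3.5.1 says "The study will reach primary completion 36 months from the time the study opens to accrual", and section 3.5.2 says "The study will reach study completion 48 months from the time the study opens to accrual".

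**Accrual.** The abstract gives "125 patients per year, for three years, giving a total of 375 patients at UCSF". Section 3.2 agrees: "It is anticipated that 125 patients per year over three years will be enrolled in this study". Section 8.2.2 keeps the rate of about 125 a year but says "Over a four-year period this will result in up to 375 patients being enrolled in the study".

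**Patient follow-up.** Section 3.4 says "Patients will be followed for one day after the administration of the radiopharmaceutical". The abstract also has a telephone call at one day. Section 5.1.1.2 e) puts the call at one to three days, the section 6.1 schedule has adverse event reporting on day 2, and section 6.1.3 has telephone follow-up to two weeks.

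**Outcome data needed later.** Section 8.3.2 b) says "All patients will be followed up 3-12 months with conventional imaging (dedicated CT, MRI and/or bone scan"). The bone and prostate-bed criteria in section 8.3.2 also use follow-up imaging up to 12 months. Section 5.1.1.1 asks for a third management survey at six months. The section 6.1 schedule lists the surveys but has no follow-up imaging and no PSA after screening.

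**The concern.** The combined reference standard of histopathology plus imaging follow-up depends on scans 3 to 12 months after PET. If the study closes when accrual ends, patients enrolled last have no time for those scans or for the six-month survey. A site that reads only section 3.4 and the schedule would not know that the scans must be collected.

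Three consequences follow.

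- **Missing reference standard.** Some late PET-positive patients would have no imaging result when the secondary PPV is calculated.
- **Classification of missing results.** Section 8.3.2 has residual rules: a PET-positive bone lesion that does not meet a true-positive criterion is a false positive, and a node that meets neither set of criteria is also a false positive. No rule covers a lesion whose follow-up has not yet happened. Read literally, a pending lesion could be counted against the PPV.
- **Primary analysis.** Under section 8.3.2 c), imaging follow-up may be used when a PET-positive node is still present after dissection. It is required when the wrong node was biopsied or bone pathology is indeterminate. Such cases arising late may be unresolved at a 36-month primary completion.

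**Working it through.** **Step 1: the plan's accrual figure.** Rate × years = total.
- Abstract and section 3.2: 125 × 3 = 375, which reproduces the stated total.
- Section 8.2.2: 125 × 4 = 500, which does not. For 375 over four years the rate would be 375 / 4 = 93.75 a year, not about 125.

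**Step 2: who is enrolled too late.** Let accrual of N patients be uniform over A months (an assumption), with closure at month C (C at least A). A patient needing f months must enter by month C − f. The share entering too late is

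max(0, A − (C − f)) / A, and the count is N times that share.

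Inputs: N = 375 (section 3.2); A = 36 (abstract, section 3.2) or 48 (section 8.2.2); C = 36 (abstract) or 48 (section 3.5.2); f = 3 and 12 (section 8.3.2) and 6 (section 5.1.1.1).

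| Accrual A | Closure C | f = 3, earliest scan | f = 6, survey | f = 12, full window |
|---|---|---|---|---|
| 36 | 36 | 3/36 = 8.3%, 31.25 patients | 6/36 = 16.7%, 62.5 | 12/36 = 33.3%, 125 |
| 36 | 48 | 0 | 0 | 0 |
| 48 | 48 | 3/48 = 6.25%, 23.4 | 6/48 = 12.5%, 46.9 | 12/48 = 25%, 93.75 |

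In the second row the last entry is at month 36 and 48 − 12 = 36, so the window just fits. There is no slack. Section 6.1 allows screening up to 30 days before imaging, so if accrual is counted at consent, a patient entered at month 36 could be scanned near month 37 and the window would close near month 49.

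**Step 3: primary completion.** Section 3.5.1 sets 36 months. With three-year accrual this is the day accrual ends, so a patient scanned in the last 3 months whose biopsy result is referred to imaging could not have a 3-month scan by then. The documents give no rate of negative or indeterminate biopsies, so the number cannot be calculated.

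**Step 4: the residual rules.** The bone and lymph node rules in section 8.3.2 turn an unmet true-positive criterion into a false positive, with no category for pending cases. The visceral and prostate-bed blocks repeat the lymph node wording, so they do not say what happens to their own unresolved lesions.

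**The case against.** The best reply is that the body of the protocol already holds a workable timeline. Section 3.2 has three years of accrual and section 3.5.2 has completion at 48 months; 36 + 12 = 48. A reader of the abstract alone might infer that the study cannot obtain its reference standard. The documents as a whole do not support that. What remains is that other statements contradict this timeline and nothing says which governs.

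A reader might also infer from section 3.4 that outcome follow-up ends at one day. Section 5.1.1.2 e) gives the purpose of the call as detecting delayed adverse events, and the schedule has a separate six-month survey column. The one-day contact is therefore most naturally safety follow-up. Section 3.4 does not say so, however, and the contact itself is given as one day, one to three days and two weeks.

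The 33% figure invites overreading. Section 8.3.2 b) asks for imaging within 3-12 months, not at 12 months. Even on the abstract's dates only about 8% would miss every qualifying scan by timing alone. The counts also cover all enrolled patients, whereas PPV concerns PET-positive patients, and biopsy-resolved cases need no imaging follow-up.

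It is tempting to claim a known bias between regions, because bone lesions can be called true positive on baseline imaging while the size criteria for nodes and visceral lesions need at least 3 months. But those lesions can also qualify through histopathology or, for solitary disease, through a PSA fall after targeted treatment, for which no minimum interval is stated. Unequal effects by region are plausible, but their size is unknown.

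Finally, section 8.3.1 restricts the primary aim to patients with histopathology, so the primary analysis is exposed only through the biopsy cases referred to imaging. That limits the problem without removing it.

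**Conclusion.** The point stands as a contradiction on timeline and follow-up. Completion is three years in one place and 48 months in another; accrual of 375 is three years in two places and four in a third, where the arithmetic fails; and the required imaging is absent from the schedule.

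The cost depends on which dates govern. With uniform accrual at the 375-patient site, none are cut short under 36-month accrual and 48-month completion. Under the abstract, about 31, 62 and 125 patients fall short of 3, 6 and 12 months; under four-year accrual with 48-month completion, about 23, 47 and 94. Scaling these to 1,500 patients would require all sites to open, accrue and close on this one timeline. No rate or opening date is given for the others, so the counts should stay at 375.

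Two smaller defects persist even on the workable dates: primary completion coincides with the end of accrual, and there is no rule for lesions still awaiting follow-up. If pending lesions were called false positives, PPV would be understated, by an amount the documents do not allow one to estimate. Confidence is high for the contradictions and low for any particular effect on the PPV.

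**What to change.** 1. Correct the abstract's completion date to match section 3.5.2 (48 months), and change the four-year period in section 8.2.2 to three years.
2. State in section 3.4 that the short follow-up is adverse-event contact only. Reconcile its length across the abstract, sections 3.4, 5.1.1.2 e) and 6.1.3, and the section 6.1 schedule.
3. Add the 3-12 month conventional imaging to the schedule. Section 8.3.2 already requires it.
4. Collect post-treatment PSA from records where available. It is an alternative true-positive criterion, and no section mandates the test, so it should not be listed as a required procedure.
5. Set the data cut-off at the last PET scan plus 12 months for the combined-reference PPV and for primary cases awaiting imaging. State whether the 36 months of accrual run to last consent or last scan, since the 30-day screening window could carry the cut-off about a month past 48.
6. State that cases still pending at the cut-off are not counted as false positives, and report their number by region.

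This is an amendment of wording, schedule and cut-off, with no new scans beyond those section 8.3.2 requires. The downside is that final results come up to 12 months later than the abstract states, apart from the possible extra month in item 5. Section 3.5.2 already foresees the 12 months.

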1.1 Overview

Imaging and staging of prostate cancer is critical for surgical and treatment planning. We aim to image patients with suspected metastatic prostate cancer using Gallium-68 labeled HBED-CC PSMA (more commonly called ^{68}Ga -PSMA-11) in order to demonstrate its utility. We plan to utilize this data to obtain further approvals of the ^{68}Ga -PSMA-11 compound, so that this agent will become available for clinical imaging in prostate cancer patients.

This compound has been shown to be superior to choline based PET agents for the staging of prostate cancer, both Carbon-11 and Fluorine-18 compounds. But this compound was not patented and therefore no company or private entity will make the investment required to bring HBED-CC PSMA to market. In the vacuum of availability, academic groups must take the lead in order to collect the necessary data for future FDA approval. This protocol was developed in collaboration with the Clinical Trials Network of the Society of Nuclear Medicine and Molecular Imaging. The inclusion criteria and study endpoints have been aligned so that inter-institutional sharing of data can be performed in order to pool data for final NDA submission..

1.2 Background

Prostate cancer is the most commonly diagnosed cancer and second leading cause of cancer death in American men (1). Existing conventional imaging (CT, MRI and bone scans) has a low sensitivity in detecting local recurrence or metastatic disease (2). The one exception being NaF PET/CT for the detection of osseous metastasis. Due to this limitation, numerous approaches to stage patients have been evaluated.

Choline imaging has been frequently used, as prostate cancer exhibits increase choline uptake that has been associated with the presence of choline kinase (3). Choline uptake is increased in comparison to FDG in both androgen dependent and independent prostate cancer patients (4). Choline has also been shown to be sensitive for the detection of recurrent tumor in patients with PSA (prostate specific antigen) values of less than 1.0 ng/ml (5). There are two forms of choline that are used in imaging prostate cancer, C-11 and F-18 choline. C-11 choline has a short half-life of 20 minutes, which limits its detection for metastatic disease but results in improved local detection due to decreased urinary activity at the time of imaging. F-18 choline has significant urinary excretion that limits evaluation of the prostate but, but has been shown to have better detection rates for distant metastatic disease (6). C-11 choline has limited sensitivity for osseous metastasis, possibly due to the decreased uptake time (7). Additionally, the sensitivity of C-11 choline is limited in patients with PSA values < 1.0 ng/ml (8-10). Although choline PET may be limited in sensitivity, it clearly delineates more lesions than cross section imaging or bone scan in patients with known disease (11). In 2012, the Mayo Clinic obtained NDA (new drug application) approval from the FDA for the use of C-11 choline.

A separate approach is to image the prostate specific membrane antigen (PSMA). PSMA is expressed on the majority of prostate cancer cells, and so would be an ideal cell membrane protein to image. The initial imaging approach to PSMA imaging target the intracellular domain using Indium-111-capromab (Prostascint), a murine monoclonal antibody (12,13). Although there was early promise for the detection of nodal metastasis (14), the agent was never able to adequately visualize osseous metastasis (15). Although combination with SPECT/CT does improve lesion detection (16). One main limitation to In-111-capromab is that it takes a prolonged time to localize to the target tissue, which likely relates to both the size of the monoclonal antibody and the fact that agent targets the intracellular domain of the PSMA protein. Additionally, Prostascint also recognizes an intracellular epitope so the antibody must cross the membrane to be effective. This likely only occurs in permeable dead or dying tumor cells.

Because of the limitations of In-111 capromab, there has been continued effort to develop agents that target the extracellular domain of the PSMA protein. The Ga-68 labeled HBED-CC PSMA compound has become of particular interest because in the last year there have been two important articles. The first demonstrates that HBED-CC PSMA has a higher sensitivity for the detection of disease than F-18 choline in a head-to-head intra-patient comparison that included 37 patients (17). The second paper looked at the sensitivity of HBED-C PSMA in the detection of metastatic lesions in patients with recurrent prostate cancer (18). Their results demonstrated a detection rate of 50% for patients with a PSA less than 1 ng/ml, and detection rate above 85% for patients with a PSA greater than 2 ng/ml. These detection rates are significantly higher than that reported by groups using choline (5).

Because of the improved resolution and image quality with PET, ability to quantitate uptake, increased sensitivity compared to choline, we intend to evaluate the utility of Ga-68 HBED-CC PSMA for the imaging of prostate cancer. We expect that the data from this study will support applications for clinical approval of this imaging agent, leading to wider availability within the United States.

Of note, although this project does not include biopsy correlation, a separate small trial is being initiated at the San Francisco VA Medical Center in pre-prostatectomy patients to determine the sensitivity and specificity of nodal uptake seen on Ga-68 HBED-CC PSMA imaging. This will help to demonstrate the specificity of imaging uptake on the PET imaging.

1.3 Patient Population

Patients with biochemical recurrence after prostatectomy or radiation therapy:

- (a) Post radical prostatectomy (RP) – AUA recommendation
 - PSA greater than 0.2 ng/mL measured more than 6–13 weeks after RP and,
 - Confirmatory persistent PSA greater than 0.2 ng/mL
- (b) Post-radiation therapy –ASTRO-Phoenix consensus definition
 - Nadir + greater than or equal to 2 ng/mL rise in PSA

2 Objectives of the Study

2.1 Primary

- Sensitivity and positive predictive value (PPV) on a per-patient and per-region-basis (Table 1) of ⁶⁸Ga-PSMA-11 PET for detection of tumor location confirmed by histopathology/biopsy.

Region	Description
1	Prostate Bed
2	Pelvis outside of prostate bed including lymph nodes
3	Extrapelvic soft tissue, lymph nodes and organ metastases (non-bone)
4	Bone metastases

2.2 Secondary

- Sensitivity and PPV on a per-patient and per-region-basis (Table 1) of ⁶⁸Ga-PSMA-11 PET for detection of tumor location confirmed by histopathology/biopsy *and* conventional imaging follow-up.

- Sensitivity, specificity, and negative predictive value (NPV) on a per-patient basis of ^{68}Ga -PSMA-11 PET for detection of tumor location confirmed by histopathology/biopsy and conventional imaging follow-up.
- Detection rates on a per-patient basis of ^{68}Ga -PSMA-11 PET stratified by PSA value (0.2 - <0.5, 0.5 - <1.0, 1.0 - <2.0, 2.0 - <5.0, 5.0).
- Impact of ^{68}Ga -PSMA-11 PET on clinical management in BCR patients.
- Inter-reader reproducibility
- Safety.

2.3 Endpoints

2.3.1 Primary Endpoints

- Per patient and per region ^{68}Ga -PSMA-11 positivity.
- Biopsy correlation.

2.3.2 Secondary endpoints

- Per patient and per region detection sensitivity using a combined histology and conventional imaging correlate
- Sensitivity, specificity and negative predictive value on a per-patient basis.
- Change in management: survey based results
- Inter-reader reproducibility
- Safety: blood pressure, heart rate, self reported adverse events

3 Study Design

3.1 Characteristics

This is a prospective, Phase 1/2, multi-center, open-label study in patients with prostate cancer. Eligible participants will undergo baseline assessments at enrollment. Study participants will receive a one-time administration of Ga-68 PSMA-11 and undergo a PET/CT or PET/MRI imaging study.

3.2 Number of Subjects

It is anticipated that 125 patients per year over three years will be enrolled in this study, for a total of 375 at UCSF. In total we aim to enroll 1,500 patients across all sites.

3.3 Eligibility Criteria

Patients must have baseline evaluations performed prior to the administration of the radiopharmaceutical and must meet all inclusion and exclusion criteria. In addition, the patient must be thoroughly informed about all aspects of the study, including the study visit schedule and required evaluations and all regulatory requirements for informed consent. The written informed consent must be obtained from the patient prior to enrollment. The following criteria apply to all patients enrolled onto the study unless otherwise specified.

